Critically, smoking rates remain staggeringly high with 16.7% of US adults (41.1 million) smoking combustible tobacco. In light of the high rates of continued use and considerable disease burden of smoking, identifying novel harm reduction strategies is a significant public health target. One possible harm-reduction strategy for combustible tobacco is substitution with electronic nicotine delivery systems (ENDS). Reduced exposure to tobacco constituents has contributed to the public health view that while ENDS are not without harm these harms are reduced relative to combustible tobacco. Importantly, in smokers unwilling to quit, providing ENDS and encouraging switching from combustible cigarettes could reduce smoking-related harms and provide opportunities for cessation without typical rates of relapse. Studies of “healthy” smokers have also shown improved pulmonary function associated with substituting combustible tobacco for ENDS.

The current study aims to evaluate the effect of a randomized controlled clinical trial of complimentary ENDS provision to adults with asthma on tobacco use behaviors (including substitution of smoking for ENDS use), pulmonary function, asthma control and symptomatology, and related inflammatory and disease outcomes over 16 weeks. This study is significant because smoking is strongly linked to respiratory diseases such as COPD and asthma and targeting adults with asthma for harm reduction could reduce the public health burden of these diseases. Furthermore, given the limited research on this target population and the difficulty of promoting smoking cessation in people

who are unwilling to quit, using ENDS to facilitate substitution of smoking for ENDS represents a novel direction for harm reduction research.

2. Specific Aims and Study Objectives. *The IRB must evaluate the objectives of the research in order to determine whether the risks to participants are reasonable in relation to the importance of the knowledge that may be gained.*

Primary Aims and Hypotheses

Aim 1a. Assess the effects of 8 weeks of complimentary ENDS provision on cigarette use, ENDS use, and nicotine dependence, among adults with asthma over a 16 week period.

Hypothesis 1. ENDS participants will smoke fewer cigarettes/day and demonstrate reduced cigarette dependence than control participants.

Aim 1b. Examine the effect of ENDS provision on respiratory function in adults with asthma.

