Hypothesis 2. ENDS participants will exhibit better asthma control and improved pulmonary function on measures of spirometry (i.e., PEF, FEV1, FVC, FEV1/FVC ratio, FEF25-75) and self-reported respiratory symptoms (wheezing, bronchitis, shortness of breath, mucus production, and other symptoms).

[figure not shown]
Secondary Aims

Aim 2a. Examine the effects of ENDS provision on inflammatory and disease biomarkers, including (IL-6, TNF- α , CXCL9, MMP9, FENO) and tobacco toxicant exposure (cotinine, CO, NNAL) at weeks baseline and week 8.

Hypothesis 4. Levels of both inflammatory biomarkers and tobacco toxicant exposure will be improved among participants randomized to ENDS relative to assessment-only control.

Aim 2b. Examine the effect of ENDS provision on intention to quit smoking and smoking cessation self-efficacy.

Hypothesis 5. ENDS participants will have higher quit intentions, and smoking cessation self-efficacy than controls.

3. Materials, Methods and Analysis. *The study design, methods and procedures must be adequately described in order for the IRB to understand all activities in which human subjects will participate. The IRB must also be able to differentiate those procedures that are performed for research purposes from those that are performed for routine care or evaluation.*

Design Overview: This study will use a between-subjects (N=30) randomized (unequally allocated 2:1), controlled design to investigating the influence of complimentary ENDS provision on combustible cigarette and ENDS use (including substitution of smoking for ENDS use), cigarette dependence, pulmonary function, and clinical indicators and biomarkers over 16 weeks. Eligible participants will be randomized to one of two conditions: 1) receive ENDS and e-liquid for 8 weeks, including encouragement to fully switch from cigarettes to ENDS; or, 2) an assessment-only control condition wherein participants may continue their usual cigarette smoking behaviors. The study involves initial and in-person screening, a baseline session and 8 weekly visits, and a 16-week follow-up visit (i.e., 8 weeks after discontinuation of complimentary ENDS provision to the experimental group).

ENDS selection: We intended to use JUUL for the ENDS condition due to its market share and nicotine delivery comparable to combustible cigarettes. However, due to shifting perceptions of JUUL related to EVALI and because the products have similar nicotine delivery profiles, we chose the VUSE Alto.

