DOCUMENT: Statistical Design and Power

PROTOCOL TITLE: Complimentary Electronic Cigarettes for Harm Reduction among Adult Smokers with Asthma

NCT: NCT05278065

DOCUMENT DATE: 06/17/2020

Statistical Design and Power

Statistical Design

Initial data analysis will include descriptive analysis for the sample and within study condition, tests of attrition, missing data analysis, evaluation of distributional properties, and correlations among measures. Potential moderators of treatment outcome (e.g., compliance) will also be examined.

Quantitative Analyses

Aim 1 - Hypothesis 1: At Week 8, ENDS participants will smoke fewer cigarettes/day (CPD) and show reduced cigarette dependence relative to BL. Relative rates of CPD reduction and cessation across study arms will be examined. DVs: cigarettes per day (from TLFB); FTCD and WISDM scores. IVs: time; condition; time by condition interaction.

Aim 2 - Hypothesis 2: ENDS participants will exhibit better asthma control and self-reported respiratory symptoms (wheezing, bronchitis, shortness of breath, mucus production) versus baseline. Changes in lung function will be explored. Primary DVs: Asthma Control: ACT scores, Asthma Symptoms: ASUI scores, Mini-AQLQ scores; Secondary DVs: Spirometry: PEF, FEV₁, FVC, FEV₁/FVC ratio, and FEF₂₅₋₇₅. IVs: time; condition; time by condition interaction.

Aim 3 - Hypothesis 3: Biomarkers of exposure, toxicity, and inflammation will be lower in ENDS participants versus BL. DVs: Inflammatory and Disease Biomarkers: IL-6, FENO, Exposure and Toxicity: NNAL, TNE, TNE/NNAL ratio. IVs: time; condition; time by condition interaction.

Qualitative Analyses

Aim 4 - Hypothesis 4: High willingness to participate, high weekly retention, low attrition, and few reported barriers to engagement will demonstrate feasibility of complimentary ENDS provision for cigarette substitution. Hypothesis 5: Positive responses during qualitative exit interviews will demonstrate acceptability.

Analytic approach:

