Multiple approaches will be used to investigate smoking/ENDS use; respiratory function; and inflammatory and disease marker outcomes but will primarily focus on developing a longitudinal model based on intent-to-treat principles. Initially, t-tests (paired and independent samples) will quantify differences in outcomes across groups or time, and ANOVA will be used to investigate within, between, and within-between interactions. We will leverage the robustness of linear mixed effects models (LMEM) or generalized estimating equations (GEE) to examine outcomes within a longitudinal framework. Intraclass correlations (ICCs) of outcome variables within participant classes will be investigated. Model terms will include time, condition, and their interaction, and covary for potentially unbalanced baseline demographic and behavioral (e.g., smoking) factors across conditions. LMEM models will include random intercepts to account for subject-level differences in outcomes and investigate fixed linear, quadratic, and subject-level random effects of time. Appropriate LMEMs will be selected based on the distributional properties of the DV. We will investigate logarithmic transformations of the outcome where necessary. DVs with high resolution data (e.g., measure of cigarettes per day available weekly), will be modeled at the weekly level. All analyses will be conducted in R version 3.6.0, using the geepack package for GEE and lme4 package for LMEMs.

Missing data:

Systematic missing data due to attrition or other factors will be examined. We will first conduct Little's MCAR test on a dataset including all participant characteristics, covariates, primary, and secondary outcomes to evaluate whether missing data patterns are consistent with the Missing Completely at Random (MCAR) assumption. As data in longitudinal studies is rarely MCAR, we will initially use the VIM package in R to identify patterns of systematic missingness across time. We will also use t-tests and χ^2 tests to examine whether covariates and outcomes at week 8 vary as a factor of attrition at subsequent time points. Multiple-imputation will be used for sensitivity analyses of all primary and secondary outcome models following identification of predictors of missingness to help sustain the missing-at-random (MAR) assumption. Multiple imputation will be conducted in the *mice* package for R.

Power Analysis and Sample Size

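### SAP Hypotheses 1 and 3 are worded as ENDS-arm change from baseline, while the matching Protocol hypotheses are claims against the randomised control

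*SAP*

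**What the plan says.** **Hypotheses.** In the Protocol (Part III, section 2), Hypothesis 1 reads "ENDS participants will smoke fewer cigarettes/day and demonstrate reduced cigarette dependence than control participants". Hypothesis 4 says that inflammatory and toxicant biomarkers "will be improved among participants randomized to ENDS relative to assessment-only control". Hypothesis 2, on asthma control and lung function, begins "ENDS participants will exhibit better asthma control and improved pulmonary function on measures of spirometry" and names no comparator.

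In the SAP (Quantitative Analyses), Hypothesis 1 reads "At Week 8, ENDS participants will smoke fewer cigarettes/day (CPD) and show reduced cigarette dependence relative to BL" and Hypothesis 3 reads "Biomarkers of exposure, toxicity, and inflammation will be lower in ENDS participants versus BL". SAP Hypothesis 2 also takes baseline as its reference.

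**Analysis.** The SAP lists time, condition and their interaction for all three quantitative hypotheses. Under Hypothesis 1 it adds "Relative rates of CPD reduction and cessation across study arms will be examined". Its Analytic approach "will primarily focus on developing a longitudinal model based on intent-to-treat principles", but begins with "t-tests (paired and independent samples) will quantify differences in outcomes across groups or time" and ANOVA before the mixed or GEE models.

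**Power.** The same text in both documents (Protocol, Sample Size Considerations; SAP, Power Analysis and Sample Size) calls N=30 adequate within the ENDS arm and inadequate between arms at d=0.65. It says the pilot will help to gauge the size of group effects. Both documents describe the biomarker effects as exploratory.

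**The concern.** A fall from baseline in the ENDS arm and a fall relative to control are different claims. The first includes anything that moves both arms: being assessed weekly, regression to the mean after selection, or the passage of time. Only the second uses the randomisation.

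On the SAP wording, a significant baseline-to-Week-8 fall among ENDS participants meets Hypothesis 1 whatever the controls do. A report that follows the SAP could call the hypothesis confirmed, and a reader of the Protocol would take that as evidence against control. The same holds for the biomarkers, with less at stake because they are exploratory. At stake is which claim the data can support.

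**Working it through.** **1. Comparators side by side**

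| Outcome | Protocol | SAP |
|---|---|---|
| Cigarettes/day, dependence | H1: control participants | H1: baseline, at Week 8 |
| Asthma control, respiratory outcomes | H2: none named | H2: baseline |
| Biomarkers | H4: assessment-only control | H3: baseline |

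The mismatch is explicit in rows one and three. Row two is only a consistency point.

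**2. Inputs**

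- N=30, allocated 2:1 (Protocol, Design Overview): 20 ENDS and 10 control.
- 10% dropout (power text): 20 × 0.9 = 18 and 10 × 0.9 = 9 completers, if dropout is even.
- d=0.65 (power text). Its units are not stated.
- Alpha and sidedness are not stated. Two-sided 0.05 is assumed.
- Size of any shared change is not given. 0.2, 0.3 and 0.5 SD of change are assumed.

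**3. The plan's own power statement.** No numerical power is given, only adequate within the arm and below 0.80 between arms. With d in SDs of change:

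- Within the arm, paired t: noncentrality = 0.65 × √18 = 2.76 on 17 df. Power is 0.74 two-sided and 0.84 one-sided.
- Between arms, two-sample t: noncentrality = 0.65 × √(18 × 9 / 27) = 0.65 × √6 = 1.59 on 25 df. Power is 0.33 two-sided.

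The between-arm half reproduces. The within-arm half depends on unstated choices: it reaches 0.80 one-sided, but not with a two-sided paired test on this scale.

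If d is in raw-score SDs with within-person correlation r, the effect in SDs of change is 0.65 / √(2(1 − r)). For r=0.3 this is 0.549, for r=0.8 it is 1.028, and two-sided between-arm power runs from 0.25 to 0.68.

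**4. Shared change with no ENDS effect.** Suppose both arms improve by c SDs of change.

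- The paired test in the ENDS arm has noncentrality c × √18 and rejects in favour of ENDS when t exceeds 2.11 (17 df).
- The between-arm test on change has noncentrality 0 for every c, so it rejects in favour of ENDS with probability 0.025.

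| c (SD of change) | c × √18 | Within-arm test favours ENDS | Between-arm test favours ENDS |
|---|---|---|---|
| 0.2 | 0.85 | 0.12 | 0.025 |
| 0.3 | 1.27 | 0.22 | 0.025 |
| 0.5 | 2.12 | 0.52 | 0.025 |

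**5. Is shared change plausible here?** The documents point both ways. The Protocol's Potential Benefits section says that taking part may raise awareness of one's smoking and so alter tobacco use, without giving a direction or size. Its Recruitment Methods section expects no change in the control arm.

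**The case against.** **The randomised comparison is already in the plan.** This stands. The interaction is listed for every quantitative hypothesis, an across-arm look at cigarettes per day is promised, and an intent-to-treat longitudinal model is the main focus. A reader might infer that the SAP drops the control arm; it does not. It leaves the between-arm term outside the wording of the hypotheses.

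**The SAP does name a comparator.** This also stands. A reader might infer that the plan sets no reference at all, but each quantitative SAP hypothesis names baseline. The plan can fairly be read as testing within-arm change and estimating the arm difference. That reading is coherent within the SAP but does not match Protocol H1 and H4.

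**The power text contradicts Protocol H1.** A reader might infer this, but the documents do not support it. Stating that a pilot lacks power for a hypothesis is disclosure, not contradiction.

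**The power gap measures the harm.** A reader might take 0.74 against 0.33 as the size of the problem. Those figures assume a true ENDS effect and no control change, so Protocol H1 is true throughout. They show the low between-arm power that the plan already admits. The harm alleged here is false support from shared change, which is what step 4 shows.

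**The shared changes are assumed.** This is correct, and it is why the table is an illustration and not a forecast.

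**Conclusion.** The point holds as a mismatch between the documents on what Hypothesis 1 claims and, for exploratory biomarkers, on what SAP H3 and Protocol H4 claim. A result that satisfies the SAP wording would not by itself support the Protocol hypothesis.

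The illustrated rates of false support, 0.12 to 0.52, rest on 18 ENDS completers, a two-sided 0.05 paired test, no ENDS effect and assumed shared changes of 0.2 to 0.5 SD. With no shared change the within-arm rate is also 0.025. The figures were worked for a two-visit test on change and not for the weekly cigarettes-per-day model.

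The weight is minor to moderate. The trial is an openly underpowered pilot, the model that answers the Protocol question is already planned, and Hypothesis 2 has no direct conflict. Confidence is high on the wording mismatch and lower on its practical size, which the documents do not allow anyone to fix.

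**What to change.** **SAP Hypothesis 1.** Name the ENDS-minus-control difference in baseline-to-Week-8 change (time-by-condition evaluated at Week 8) as the contrast for each of cigarettes per day, FTCD and WISDM. Report each as an estimate with a 95% CI. With three outcomes, no single contrast decides the hypothesis, so the text should not imply that one does.

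**SAP Hypothesis 3.** Use the same contrast as an exploratory estimate.

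**Time points.** The sponsor should reconcile Week 8 in SAP H1 with the 16-week period in Protocol Aim 1a. It should also state the time point for H2, since the SAP gives none and Protocol Table 1 schedules ACT and ASUI at Weeks 8 and 16.

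**Within-arm change.** Keep it, labelled descriptive and as not using the randomised comparison.

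**Power text.** Keep the statement that between-arm power is below 0.80. If a figure is added, give it as a range with its assumptions: about 0.33 if d=0.65 is in SDs of change, or 0.25 to 0.68 if it is in raw-score SDs with r from 0.3 to 0.8 (18 v 9 completers, two-sided 0.05). Say that it does not apply to the weekly cigarettes-per-day model.

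**Cost.** Text edits only, with no new data, visits or models. The downside is that the named contrast is the one the plan already calls underpowered, so wide intervals should be expected. If the sponsor prefers within-arm change as the pilot question, Protocol H1 and H4 would need rewording to match, and both documents should say that this does not use randomisation.

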Tobacco use outcomes: Power and sample size calculations were conducted in GPower 3.1 based on between- and within-subjects analyses. [name] pilot trial examining 6 weeks of complimentary ENDS provision on tobacco use behaviors and nicotine dependence at weeks 6 and 10 (i.e., 4 weeks after final ENDS provision) found significant reductions between baseline and both time points in average cigarettes per day (baseline=19.6(8.2); week 6=6.7(7.9), $d=1.64$; week 10=8.8(8.3), $d=1.12$) and cigarette dependence (baseline=5.94(1.96); week 6=3.89(2.78), $d=.88$; week 10=3.50(3.08), $d=1.03$); all with large effects. However, given the unknown effect of providing free ENDS to adult smokers with asthma and the limited interpretability of effect sizes from pilot trials we chose to use a more conservative medium-large ($d=0.65$) effect size. With our planned enrollment ($N=30$), anticipated 10% dropout, and target power ($1-\beta=.8$), sample size was adequate to detect within-subject repeated measures (Aim 1) differences in the intervention (ENDS) group but was inadequate to detect between-subjects effects (i.e., group differences). Although power is below .80 to detect group differences, this pilot proposal will help determine the magnitude of these effects and inform the design of future research.

Respiratory outcomes: Investigations of respiratory symptoms and lung function change in 'healthy' smokers switching to ENDS have found very large ($h=1.94$) within-subjects effects for cough, very large ($h=1.50$) within-subjects effects for shortness of breath, and large ($d=.998$) within-subjects effects for FEF₂₅₋₇₅; also found were large ($d=.921$) between-subjects effects comparing successful to failed switchers. As these improvements may be even more pronounced for adults with asthma, the current planned enrollment achieves adequate power to examine these within-subjects (but not between-subjects) outcomes within the ENDS condition per the power and sample size analyses outlined above (Aim 3). However, analysis of spirometry are limited by the short follow-up period for the proposed pilot within-which changes in these metrics are not anticipated. As with the tobacco use outcomes, although power is below .80 to detect group differences, this pilot proposal will help determine the magnitude of these effects and inform the design of future research.

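### The SAP allows LMEM or GEE as its main longitudinal model with no rule for choosing and no small-sample method, and with 30 participants the two are not interchangeable

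*SAP*

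**What the plan says.** The Analytic approach section of the SAP opens with "Multiple approaches will be used to investigate smoking/ENDS use" and the other outcomes, then in the same sentence places the main emphasis on an intention-to-treat longitudinal model. Simple tests come first: "Initially, t-tests (paired and independent samples) will quantify differences in outcomes across groups or time", followed by ANOVA. For the longitudinal model it says "We will leverage the robustness of linear mixed effects models (LMEM) or generalized estimating equations (GEE) to examine outcomes within a longitudinal framework".

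The LMEM is to have random intercepts; linear and quadratic time and random time effects are to be explored. For GEE the SAP names only the R package. It states no working correlation, standard-error type, small-sample correction or reference distribution, and no degrees-of-freedom method for the LMEM.

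The Missing data section remarks "As data in longitudinal studies is rarely MCAR". It assigns multiple imputation, under MAR, to sensitivity analyses of the primary and secondary outcome models.

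**The concern.** LMEM and GEE are offered as equivalents, but they differ in two ways that matter in this trial.

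- **Sample size.** The sandwich variance used with GEE relies on a large number of participants. Here there are 30, only 10 of them in the control arm. Without a correction, the standard errors are too small and the p-values and intervals too optimistic.
- **Missing data.** A likelihood-based LMEM is valid under MAR if its mean and covariance are right. Unweighted GEE is not generally valid under MAR, and the main analysis has no imputation or weighting to make up for that.

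The trial is a pilot meant to gauge effect sizes for later research. Biased estimates and intervals that are too narrow would damage that output directly.

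**Working it through.** **Inputs from the documents**
- Protocol, Section 3, Design Overview: "This study will use a between-subjects (N=30) randomized (unequally allocated 2:1), controlled design". This gives 20 ENDS and 10 control.
- SAP, Power Analysis and Sample Size: "With our planned enrollment ($N=30$), anticipated 10% dropout, and target power". 30 x 0.9 = 27 completers, or 18 and 9 if dropout is equal by arm (assumed).
- Same section: "we chose to use a more conservative medium-large ($d=0.65$) effect size". I use -0.65 SD as the true time-by-condition effect, which is an assumption.

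**Other assumptions:** two-sided alpha 0.05 (the SAP states none), normal outcomes, within-person correlation 0.5.

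The SAP gives no standard error or error rate for either model, so there is no figure of its own to reproduce on this point.

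**Step 1. How small the uncorrected sandwich variance is.** With complete balanced data, a time contrast reduces to one value per participant, and the GEE interaction is the difference between the arm means of that value. With unit variance:

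- expected sandwich variance = (n1 - 1)/n1² + (n0 - 1)/n0²
- true variance = 1/n1 + 1/n0

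At 18:9: 17/324 + 8/81 = 0.0525 + 0.0988 = 0.151, against 0.0556 + 0.1111 = 0.167. The ratio is 0.907, and its square root 0.953. The average standard error itself is 0.94 of the truth.

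At 20:10: 19/400 + 9/100 = 0.1375, against 0.150. The ratio is 0.917, and its square root 0.957. The average standard error is again about 0.94 of the truth.

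**Step 2. Type I error, nominal 5%.** The first and third rows come from 1,000,000 random draws, the others from the formula shown.

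| Test | 18:9 | 20:10 |
|---|---|---|
| GEE interaction, uncorrected sandwich, z | 7.9% | 7.6% |
| LMEM, Wald z: 2P(t > 1.96) on n1 + n0 - 2 df | 6.1% | 6.0% |
| Corrected variance, Satterthwaite t | 5.0% | 5.0% |
| GEE within ENDS only: 2P(t > 1.96√((n-1)/n)) on n - 1 df | 7.4% (n=18) | 7.1% (n=20) |

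The last row matters because SAP Hypotheses 1 to 3 are worded as change from baseline in the ENDS arm. At 180:90 the first row falls to 5.3%, so this is a small-sample effect. GEE fits to 4,000 simulated trials at 18:9, over two-visit, three-visit and weekly layouts, gave 6.7% to 7.9%. At 20:10, a three-visit layout and two weekly layouts gave 7.3%, 7.8% and 8.3%. The Monte Carlo standard error is about √(0.079 x 0.921/4000) = 0.4 points.

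**Step 3. Bias under MAR dropout.** True interaction -0.65 SD, 100,000 simulated participants per arm, the same dropout rate in both arms, dependent on the last observed value in the ENDS arm only.

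| Dropout, data structure | GEE, independence | GEE, exchangeable | Likelihood, correct covariance |
|---|---|---|---|
| 10%, exchangeable | -0.72 | -0.65 | -0.65 |
| 10%, random slopes (SD 0.7) | -0.75 | -0.68 | -0.66 |
| 30%, exchangeable | -0.85 | -0.65 | -0.65 |
| 30%, random slopes (SD 0.7) | -0.91 | -0.70 | -0.65 |

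Only 10% is the plan's figure; 30% is a stress case. In the first row, independence GEE exaggerates the effect by 0.07/0.65 = 11%.

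**Step 4. Does choosing between the two models add error?** In 40,000 null trials (nine weekly values, intraclass correlation 0.6), uncorrected GEE or LMEM with a t reference was significant in 8.2-8.7% at 18:9 and 7.8-8.3% at 20:10. GEE alone gave 8.1% and 7.7%. The choice itself therefore adds at most about 0.6 points; nearly all the inflation comes from the GEE branch.

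**The case against.** Several points on the other side stand.

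- A reader might infer that the primary analysis is open among t-tests, ANOVA, LMEM and GEE. The SAP does not support that: the simple tests are an initial step, and the emphasis is on the longitudinal model. The open choice is between LMEM and GEE.
- A reader might infer that GEE requires MCAR. That is too absolute. With a correct exchangeable working correlation, the bias at the planned 10% dropout is negligible. The difficulty is that the SAP specifies no working correlation.
- A reader might infer that the GEE standard errors in this trial will be too small. That holds only for an uncorrected sandwich with a z reference, and the SAP does not say what it will use. LMEM with a Wald z test is also mildly anti-conservative, so part of the gap is z against t rather than GEE against LMEM.
- Intention-to-treat models can use available data from all 30 participants, so 20:10 is as relevant as 18:9. The result hardly changes.
- Per Protocol Table 1, only the timeline follow-back and the Mini-AQLQ, among the SAP's outcome measures, are collected weekly. The small-sample problem does not depend on the number of visits, however.
- The planned imputation could expose dropout bias, but only after the main result is fixed.
- This is a pilot with conceded low between-arm power. That lowers the stakes for significance testing, but not for estimates and intervals.

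The bias is also modest beside the noise. With correlation 0.5 the change-score SD is √(2 x 0.5) = 1, so the standard error at 20:10 is √0.15 = 0.39, and 0.07 is about a fifth of it.

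**Conclusion.** The concern holds in a limited form. The SAP leaves its main model as LMEM or GEE, and one permitted version (uncorrected sandwich, z reference) has a type I error of about 7.5-8% instead of 5%. LMEM with Wald z reaches about 6%, so naming LMEM without a degrees-of-freedom method would not fully close the gap. Under one illustrative MAR mechanism at 10% dropout, the estimate moves from -0.65 to about -0.72 SD with an independence working correlation, and barely moves with a correct exchangeable one.

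These figures assume two-sided 5% tests, normal outcomes and, for the bias, a dropout mechanism that the documents do not describe. The advantage of LMEM also depends on its covariance: a random-intercept model implies the same exchangeable structure as exchangeable GEE.

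A reader might go further and ask for the Week 8 between-arm contrast as the main estimate. That does not follow from this point. SAP Hypotheses 1 to 3 are worded against baseline, and between-arm power is acknowledged to be low.

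**What to change.** In the SAP's Analytic approach section:

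1. Name the LMEM fitted by REML, with time, condition and time-by-condition, as the main model, with Kenward-Roger or Satterthwaite degrees of freedom for tests and intervals.
2. State that t-tests and ANOVA are descriptive.
3. Keep GEE as a sensitivity analysis with a stated working correlation, a small-sample-corrected variance (for example jackknife) and a t reference, fitted to the multiply imputed data sets.

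This changes SAP wording only; it needs no extra participants, visits or data. Intervals become slightly wider: on 25 degrees of freedom the multiplier is 2.06 instead of 1.96, about 5% more. The team also loses some freedom to switch methods.

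### Between-arm contrasts make no use of each outcome's own baseline value: this costs precision for cigarettes per day, though not for dependence, and the SAP should state the role of baseline

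*SAP*

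**What the plan says.** Under Quantitative Analyses the SAP gives each of Aims 1 to 3 the same predictors: "IVs: time; condition; time by condition interaction". Under Analytic approach the terms are again "Model terms will include time, condition, and their interaction", and the model will "covary for potentially unbalanced baseline demographic and behavioral (e.g., smoking) factors across conditions". On random effects and the form of time: "LMEM models will include random intercepts to account for subject-level differences in outcomes and investigate fixed linear, quadratic, and subject-level random effects of time". For frequently measured outcomes: "DVs with high resolution data (e.g., measure of cigarettes per day available weekly), will be modeled at the weekly level".

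Nothing states whether the baseline value of an outcome is a response or a covariate. No common baseline mean is imposed, and no outcome's own baseline is named as a covariate.

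Several passages bear on which was meant:

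- The hypotheses are framed against baseline, for example "At Week 8, ENDS participants will smoke fewer cigarettes/day (CPD) and show reduced cigarette dependence relative to BL".
- Analytic approach plans an ANOVA with within, between and within-between effects.
- Protocol Aim 2a examines biomarkers "at weeks baseline and week 8". Protocol Table 1 shows the blood markers at those two visits only.
- Protocol section 3 (Baseline Visit) places randomisation after the baseline measures are completed.

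**The concern.** For a blood marker measured only at baseline and week 8, a time-by-condition term exists only if baseline is one of the responses. For the other outcomes the same reading is strongly implied. The model then estimates an arm difference at baseline that randomisation has already made zero in expectation, and the interaction carries that estimate's noise.

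The covariate clause appears to deal with chance imbalance in baseline smoking. A covariate that is constant over time shifts all of a participant's values equally, so it cancels from within-person change. The text therefore promises an adjustment that the term of interest does not receive.

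At stake is the precision of the between-arm estimate. The SAP concedes low power for group differences but says that the pilot will help determine their magnitude. Hypothesis 1 in the protocol is itself a comparison with controls.

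**Working it through.** **Inputs.** N = 30 and the 2:1 allocation come from Protocol section 3 (Design Overview). The 10% dropout, d = 0.65 and the pilot results come from the SAP power section. 20:10 less 10% gives 18:9, or 27 completers. Alpha and sidedness are not stated; I assume two-sided 0.05. No baseline-to-follow-up correlation r is given.

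**The plan's own figure.** The SAP says that between-arm power is below .80. A two-sample t test at 18:9 with d = 0.65 has noncentrality 0.65/√(1/18 + 1/9) = 0.65/0.408 = 1.59 on 25 df. Power is 0.33 two-sided (0.46 one-sided), so the statement reproduces.

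**Do the covariates reach the interaction?** Random-intercept models were fitted to simulated 18:9 data.

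| Design | Interaction, no covariates | With baseline covariates | With own baseline added | Raw difference in mean change at week 8 |
|---|---|---|---|---|
| Baseline, week 8 (categorical) | -1.034 | -1.034 | -1.034 | -1.034 |
| Baseline, weeks 8 and 16 (categorical) | -0.767 | -0.767 | -0.767 | -0.767 |
| Weekly, linear time | -0.0489 | -0.0489 | -0.0489 | not the same estimand (slope) |
| Weekly, linear time, about 20% at risk of dropout | -0.0254 | -0.0284 | -0.0253 | not the same estimand (slope) |

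With complete data the estimate does not move. With dropout the weekly estimate moves slightly. The standard error is less stable: in the two-visit fit, entering own baseline as a covariate while it was also a response changed it from 0.447 to 0.367 without changing the estimate.

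**Correlation implied by the pilot.** The figures start with "baseline=19.6(8.2); week 6=6.7(7.9" for cigarettes per day. If each d is mean change D over SD of change, then SD of change = D/d and r = (s0² + s1² − (D/d)²)/(2·s0·s1). For week 6, D/d = 12.9/1.64 = 7.87 and r = (67.24 + 62.41 − 61.87)/129.56 = 0.52.

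**Variance ratio, own-baseline adjustment over change score.** The ratio is s1²(1 − r²)/(D/d)². Estimating the slope with 27 participants multiplies it by 1 + 1/(27 − 4) = 1.043. For week 6 cigarettes per day: 62.41 × (1 − 0.523²)/61.87 = 0.73, and 0.73 × 1.043 = 0.76.

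| Outcome | s0, s1 | D/d | r | Ratio | Net ratio | Power, change score | Power, adjusted |
|---|---|---|---|---|---|---|---|
| Cigarettes/day, week 6 | 8.2, 7.9 | 7.87 | 0.52 | 0.73 | 0.76 | 0.33 | 0.42 |
| Cigarettes/day, week 10 | 8.2, 8.3 | 9.64 | 0.32 | 0.67 | 0.69 | 0.33 | 0.45 |
| Dependence, week 6 | 1.96, 2.78 | 2.33 | 0.56 | 0.97 | 1.01 | 0.33 | 0.33 |
| Dependence, week 10 | 1.96, 3.08 | 2.37 | 0.64 | 1.00 | 1.04 | 0.33 | 0.32 |

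Power is for an effect of 0.65 SD of change. Simulations of 20,000 trials per row agree within simulation error (variance ratios 0.76-0.77, 0.69, 1.01, 1.05), with type I error at 5% for both methods.

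**Why the two outcomes differ.** The best multiplier for baseline is r·s1/s0; a change score fixes it at 1. For cigarettes per day the multiplier is 0.523 × 7.9/8.2 = 0.50 at week 6 and 0.317 × 8.3/8.2 = 0.32 at week 10. For dependence it is 0.564 × 2.78/1.96 = 0.80 and 0.639 × 3.08/1.96 = 1.00, so the change score is already close to optimal.

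**Other outcomes.** With equal SDs the ratio is (1 + r)/2, times 1.043. For an effect of 0.65 follow-up SD:

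| r | Net variance saving | Power, change score | Power, adjusted |
|---|---|---|---|
| 0.3 | 32% | 0.25 | 0.35 |
| 0.5 | 22% | 0.33 | 0.41 |
| 0.6 | 16% | 0.40 | 0.46 |
| 0.9 | 1% | 0.93 | 0.93 |

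**The case against.** The SAP's own Hypotheses 1 to 3 are stated as changes within the ENDS arm, and it admits that between-arm power is inadequate. An unconstrained time-by-condition model is unbiased under randomisation and keeps its type I error. Own-baseline adjustment is therefore an efficiency refinement, and no planned conclusion is shown to be invalid. That stands, and it limits the severity.

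The role of baseline is also inferred. For weekly cigarettes per day, the covariate clause could be read as baseline smoking adjusted for, with post-baseline weeks as responses, which is close to the fix below. That reading is open for this outcome, is not available for the blood markers, and is the reason to ask for an explicit statement.

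Three stronger readings are tempting, and the documents do not support them:

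- A reader might infer that every outcome loses precision. The pilot SDs show no loss for dependence, and highly correlated measures would lose almost nothing.
- A reader might infer that the interaction is always a change-score contrast. That needs categorical time; under linear or quadratic weekly time it is a slope or curve contrast.
- A reader might infer that covariates can never alter the estimate or its standard error. The estimate result needs complete data and an identity link, while the SAP expects 10% dropout and lets the outcome's distribution choose the model. The standard error can change even with complete data.

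**Conclusion.** The point holds as one of efficiency and specification. On the most plausible reading, the between-arm term estimates a baseline difference known to be zero, and the planned adjustment for baseline smoking essentially does not reach it.

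For cigarettes per day the avoidable variance is about 23-31%: the 27 completers would do the work of roughly 35 to 39 (27/0.77 and 27/0.69). For dependence there is nothing to recover. For the remaining outcomes the size depends on a correlation that the documents do not give.

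These figures rest on the assumptions listed above, chiefly that the pilot d values are mean change over SD of change and that asthma participants resemble the pilot sample in spread and correlation. A reader might infer that the change rescues the between-arm test. It does not: power for cigarettes per day stays at about 0.45 or less. The gain is a tighter estimate of the effect that the pilot is meant to size.

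**What to change.** State in Analytic approach whether baseline is a response or a covariate for each outcome. For between-arm contrasts, specify one of two forms:

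1. A common-baseline model: time coded from 0 at baseline, with time and time-by-condition terms but no condition main effect. The within-ENDS change is still read from the same fit.
2. A model of post-baseline visits with the outcome's own baseline value, and its interaction with visit, as covariates.

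In form 1 a random intercept alone forces equal variance at all visits, so the covariance structure should be stated too.

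The cost is a sentence or two in the SAP. Every outcome's baseline value is already collected. Statistically it costs one degree of freedom per slope and, for outcomes whose SD rises at follow-up, at worst a few percent of variance.
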